#### **4.3.2 Secondary Efficacy Endpoints**

##### **4.3.2.1 Number of patients within stable range of Hb**

The number of patients with an average Hb concentration during the evaluation period within  $\pm 1$  g/dL of their baseline Hb or above, within, or below the range of 10-12 g/dL and those who fulfill both criteria will be summarized. The classification of each patient will be based on their average Hb for the baseline and evaluation periods as calculated for the primary endpoint.

##### **4.3.2.2 Change in Mircera dose over time**

The change in Mircera dose over time, including the change between the starting dose and the evaluation period, will be analyzed descriptively, overall and by age-group. The ratio of starting dose (Week 1) to the dose at the evaluation period (Week 17) will be summarized by using mean, median, minimum and maximum.

A dose change is defined as a change in the administered dose strength compared to the preceding dose. The number of patients with dose increases, dose decreases and both increases and decreases will be tabulated.

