4.3.1 Study Treatment Formulation, Packaging, and Handling

Mircera will be provided by the Sponsor in sterile injectable solution in single-use, prefilled syringes (PFS). The Mircera solution is formulated in sodium phosphate, sodium sulfate, mannitol, methionine, and poloxamer 188, pH 6.2. This formulation does not contain any preservative.

The PFS is available in the following strengths:

30	50	75	100	120	150	200	250	µg/0.3 mL
----	----	----	-----	-----	-----	-----	-----	-----------

360	µg/0.6 mL
-----	-----------

The PFS should be stored in a refrigerator at 2°C–8°C (35.6°F–46.4°F) and protected from light. The investigational site is responsible for maintaining a daily temperature log of this refrigerator.

For information on the formulation and handling of Mircera, see the Mircera Investigator's Brochure and the local prescribing information for Mircera.

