4.3.2.1 Rationale for Starting Dose Selection

The starting dose will be based on CFs obtained from the dose-finding study (Study NH19707) (see Section 3.3.1). The initial dose of Mircera will be one of nine starting doses corresponding to the PFS strengths based on the total weekly ESA dose during the screening period, as described in Table 2.

Table 2 Mircera Starting Dose

Previous Weekly Epoetin Alfa or Epoetin Beta Dose [IU/Week]	Previous Weekly Darbepoetin Alfa Dose [μ g/Week]	Every 4-week Mircera Dose [μ g]
< 1300	< 6	30
1300– <2000	6– <9	50
2000– <2700	9– <12	75
2700– <3500	12– <15	100
3500– <4200	15– <19	120
4200– <5500	19– <24	150
5500– <7000	24– <31	200
7000– <9500	31– <42	250
\geq 9500	\geq 42	360

Once 12 patients have completed 20 weeks of treatment, an interim analysis to assess the pharmacokinetics, efficacy, and safety will be performed (see Section 6.9). If the results of this interim analysis indicate that the starting dose is not appropriate, then it may be changed (see Section 6.9).

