4.3.2.1.1 Dose Adjustments of Mircera

Dose adjustments may be performed during the entire study. The dose of Mircera should be adjusted to maintain the individual patient's Hb within a target range of ± 1 g/dL of his or her baseline Hb and between 10.0–12.0 g/dL. Baseline Hb is calculated as the mean of Hb values obtained at Visit 1 (Week –3) and Visit 2 (Week –1).

Dose adjustments should be performed at the scheduled dosing days and should be based on the Hb value measured on that day. They should not be performed more often than once every 4 weeks.

Dose adjustment rules for Mircera in response to Hb changes, including those required for safety reasons, are summarized in [Table 3](#).

Table 3 Mircera Dose Adjustments

Hemoglobin Assessment	Compared with the Previous Mircera Dose
Hb decreases by more than 1.0 g/dL compared with baseline Hb.	Increase dose by approximately 25% (or closest higher PFS strength).
Hb is less than 10 g/dL and greater than or equal to 9 g/dL (Hb < 10.0 and ≥ 9.0 g/dL).	Increase dose by approximately 25% (or closest higher PFS strength).
Hb is less than 9 g/dL (Hb < 9.0 g/dL).	Increase dose by approximately 50% (or closest to 50% increase PFS strength).
Hb increases by more than 1.0 g/dL compared with the baseline Hb.	Decrease dose by approximately 25% (or closest lower PFS strength).
Hb is increasing and is approaching 12 g/dL or Hb is greater than or equal to 12 g/dL (Hb ≥ 12 g/dL).	Decrease dose by approximately 25% (or closest lower PFS strength).
If Hb exceeds 12 g/dL and continues to increase following a dose reduction.	Stop doses until Hb is less than 12.0 g/dL. Resume dose at approximately 25% below previous dose (or closest lower PFS strength) at next scheduled dosing day.

Hb = hemoglobin; PFS = *prefilled syringe*..

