#### **4.3.1 Primary Efficacy Endpoint**

Hb concentration values (g/dL) over time and change in Hb from baseline to evaluation period will be presented in summary tables and graphically. The estimates will be summarized descriptively using means, standard deviation and percentiles.

The individual change from baseline will be reported using summary statistics (including mean, standard deviation and 90% CI of mean change). No formal statistical testing will be performed. Additional analysis will be performed by age category (<5, 5-11, ≥12 years), dialysis type (not yet on dialysis, PD, HD) and previous ESA (epoetin [epoetin alfa or epoetin beta or biosimilar] or darbepoetin alfa), if numbers allow.

The 90% confidence interval (CI) for the average per-patient Hb change from baseline to the evaluation period (weeks 17-21) will be calculated. If the lower limit of the CI is ≥-1 g/dL, the upper limit ≤1 g/dL and the number of dose increases and decreases are approximately balanced across the patients the conversion factor from prior ESA treatment for the first Mircera dose will be considered appropriate.

The Hb change from baseline is calculated on a per-patient basis, using an Area Under the Curve (AUC) approach to calculate an individual's average for both the baseline and evaluation periods and taking the difference. This per-patient change is then averaged over all patients and the confidence interval calculated.

The baseline period is defined as all assessments between the day of first study dose and the previous 35 days. If during the baseline period Hb measurements  $H_0, \dots, H_n$  are taken at timepoints  $t_0, \dots, t_n$ , a time adjusted average baseline Hb value will be calculated by

$$y = \frac{1}{2(t_n - t_0)} \sum_i (H_i + H_{i-1})(t_i - t_{i-1})$$

The value on the day of the first dose is included in the baseline calculation, as this assessment will be performed before the first dose is given.

The average Hb value for each individual during the evaluation period will be calculated using the same method as for the baseline period. The evaluation period is defined as all assessments between Visit 8 (Week 17) and Visit 10 (Week 21) inclusive. Subtracting the baseline period value from the evaluation period value gives the change in Hb concentration (g/dL) between the baseline and evaluation period.

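### A dose decrease indicated at 30 µg has no lower strength to move to and is scored as no change, so the dose-balance condition for the conversion factor can understate decreases.

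*SAP*

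**What the plan says.** SAP 4.3.1 sets a two-part rule for judging the conversion factor. The first part concerns the 90% confidence interval of the mean Hb change: "If the lower limit of the CI is ≥-1 g/dL, the upper limit ≤1 g/dL". The second requires that "the number of dose increases and decreases are approximately balanced across the patients". No numerical limit is given for the second part.

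SAP 4.3.2.2 supplies the definition that feeds it: "A dose change is defined as a change in the administered dose strength compared to the preceding dose". The planned table is by patient: "The number of patients with dose increases, dose decreases and both increases and decreases will be tabulated". Dose change and dose adjustments are also summarised by age group (SAP 4.3.2.2 and 4.3.2.4).

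Protocol 4.3.1 lists nine strengths: 30, 50, 75, 100, 120, 150, 200, 250 and 360 µg. Protocol 4.3.2.1 uses the same nine as starting doses: "The initial dose of Mircera will be one of nine starting doses corresponding to the PFS strengths". The lowest band in Table 2 (under 1300 IU/week of epoetin, or under 6 µg/week of darbepoetin) and the highest (9500 IU/week or more, or 42 µg/week or more) are open-ended.

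Protocol Table 3 (4.3.2.1.1) asks for a decrease when Hb is more than 1.0 g/dL above baseline, or is at or rising towards 12 g/dL: "Decrease dose by approximately 25% (or closest lower PFS strength". It makes no exception at 30 µg for decreases or at 360 µg for increases. The row that stops dosing has its own condition: "If Hb exceeds 12 g/dL and continues to increase following a dose reduction".

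**The concern.** The balance condition is there to show whether the starting dose was systematically too high or too low. That works only if a patient who needed less is as likely to be counted as a patient who needed more. At 30 µg this fails, because the downward move does not exist and the upward move does.

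The gap matters most in any subgroup where 30 µg is common. Use in children under 6 years is one of the questions the study was set up to answer (Protocol 1.3). Young children may well be concentrated in the lowest band, but that is an inference, since Table 2 assigns by previous weekly ESA dose and not by age or weight. The ratio of starting dose to Week 17 dose in SAP 4.3.2.2 has the same one-sided limit: for a 30 µg starter who is dosed at Week 17 it can equal 1 or fall below 1 (30/50 = 0.60), but cannot exceed 1.

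**Working it through.** **1. The plan's own figure.** The only calculation behind the two-part rule is in Protocol 6.1 and SAP 2.3: about 90% power with 26 patients, SD 1.5 and true change 0.
- SE = 1.5/√26 = 0.294; the 95th percentile of t on 25 df is 1.708; half-width = 1.708 × 0.294 = 0.502.
- Power = 2Φ((1 − 0.502)/0.294) − 1 = 2Φ(1.691) − 1 = 90.9%. With the SD estimated, simulation gives 90.3%.

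The figure is reproduced. It concerns the interval only; the balance condition has no calculation behind it.

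**2. Table 3 against the strength list.**

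| Strength | −25% | Next lower | +25% / +50% | Next higher |
|---|---|---|---|---|
| 30 µg | 22.5 | none | 37.5 / 45 | 50 (+67%) |
| 50 µg | 37.5 | 30 (−40%) | 62.5 / 75 | 75 (+50%) |
| 250 µg | 187.5 | 200 (−20%) | 312.5 / 375 | 360 (+44%) |
| 360 µg | 270 | 250 (−31%) | 450 / 540 | none |

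Every strength between the ends has a step both ways. The stop row does not clearly cover the bottom end. It presupposes an earlier reduction, which a patient who has stayed on 30 µg has not had, and it restarts at a lower strength.

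**3. Where the lowest band sits relative to the factor.** The epoetin factor is 4 × weekly IU/125 (Protocol 3.3.1). It equals 30 µg at 30 × 125/4 = 937.5 IU/week. At 500 IU/week it gives 16 µg, so the table dose is 30/16 = 1.9 times the factor value. At 1299 IU/week it gives 41.6 µg, so the table dose is 0.72 of it. The band thus contains patients on both sides of the factor, and those on the high side are where a decrease cannot register.

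**4. Size, by illustration.** Assumptions, none of them from the documents: at each of the four later doses (Weeks 5, 9, 13, 17) an increase is indicated with probability 0.20 and a decrease with probability 0.20, independently; each indicated change moves one strength if one exists; a fraction f starts on 30 µg; the rest start mid-range (120 µg). The cohort is 40 × 0.7 = 28.
- Mid-range starter: 4 × 0.20 = 0.80 expected increases and 0.80 expected decreases.
- 30 µg starter: 0.80 increases. A decrease is possible only when above 30 µg, which has probability 0, 0.20, 0.32 and 0.40 at the four doses. Expected decreases = 0.20 × (0 + 0.20 + 0.32 + 0.40) = 0.184.
- Recorded ratio D/U = [0.80(1 − f) + 0.184f]/0.80 = 1 − 0.77f.

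SAP 4.3.2.2 tabulates patients, so the same exercise is needed per patient. The chance of at least one recorded change is 1 − 0.8⁴ = 0.590 in each direction for a mid-range starter and for increases in a 30 µg starter. For a 30 µg starter the chance of no recorded decrease is 0.8⁴ + 4 × 0.2 × 0.8³ = 0.410 + 0.410 = 0.819, so at least one has probability 0.181. The ratio is 1 − (0.590 − 0.181)f/0.590 = 1 − 0.69f.

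| Start on 30 µg (none on 360 µg) | D/U, events (28 patients) | D/U, patients |
|---|---|---|
| 5% | 0.96 (21.5/22.4) | 0.97 |
| 10% | 0.92 (20.7/22.4) | 0.93 |
| 20% | 0.85 (19.0/22.4) | 0.86 |
| 30% | 0.77 (17.2/22.4) | 0.79 |

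The true ratio is 1.00 in every row. With 10% on 360 µg only, and increases blocked there, the event ratio is 1/(1 − 0.077) = 1.08. With 10% at each end it is 1.00.

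If decreases are indicated twice as often as increases (0.30 against 0.15), the true event ratio of 2.00 is recorded as 1.83, 1.67 and 1.50 with 10%, 20% and 30% on 30 µg.

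**The case against.** The strongest reply is that the planned endpoint is change in Mircera dose, and recording no change when none was given is accurate. Over-dosing is also visible elsewhere. Uncorrected Hb drift enters the mean change and its interval. Patients above 12 g/dL are counted, and every patient's Hb change is listed (SAP 4.3.2.3). The primary endpoint is repeated by age group (SAP 4.3.5). All of this stands. It limits the harm, but it does not repair the balance condition, which the SAP requires in addition to the interval and which does not see blocked decreases.

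Three stronger readings are tempting and are not supported.
- A reader might infer that the verdict is distorted, or that an excessive starting dose would look balanced or even too low. That follows in a cohort placed wholly on 30 µg, but about 10–15 of at least 40 patients are to be under 12 years, and the share on 30 µg is not stated. In the mixed illustration a twofold excess of decreases stays visible. With no limit for approximate balance, a reversed verdict cannot be demonstrated.
- A reader might infer that increases at 360 µg cannot be recorded. Protocol 4.3.2 describes injection with a prefilled syringe and bars reuse of it, but does not expressly exclude a second syringe.
- A reader might infer that sites must leave 30 µg unchanged. Protocol 4.5 permits dosing only when clinical and laboratory findings are acceptable, so a dose may be withheld. The SAP does not say whether that is a dose change.

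**Conclusion.** The point holds as a one-sided blind spot at the bottom of the strength range. It rests on the text alone: a decrease indicated at 30 µg, with the strength left unchanged, is not counted, while an increase from 30 µg is. At 360 µg it is conditional on one syringe per dose.

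The size is uncertain. Under the stated probabilities the recorded ratio falls from 1.00 to between 0.96 and 0.77 by events (0.97 to 0.79 by patients) for 5% to 30% starting on 30 µg and none on 360 µg. It moves back towards 1.00 if the top end is also populated and blocked. The effect would be larger within an age group where 30 µg predominates. The interval condition and its power are unaffected. The change is worth making because it corrects a criterion of the verdict using data already collected.

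**What to change.** Keep the administered-strength count as defined. In SAP 4.3.2.2 and 4.3.2.4, overall and by age group, add:
1. the number of patients, each counted once per direction, for whom pre-dose Hb at Week 5, 9, 13 or 17 indicated a Table 3 increase or decrease that was not possible at 360 or 30 µg, using the Table 3 baseline (mean of Visits 1 and 2);
2. an explicit statement of how a withheld dose is classified.

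In SAP 4.3.1, read the balance condition twice: as now, and with blocked patients added to their indicated direction unless already counted there.

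Do not replace the count with raw visit-level triggers. A patient held at 30 µg with high Hb can trigger at all four visits, while one whose dose is lowered may trigger once, so such a count could suggest over-dosing even with a suitable starting dose.

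The cost is one derived flag from Hb and dose data already on the eCRF. The Table 3 row for Hb approaching 12 g/dL must be left out or given a programmable form.

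Separately, the sponsor should reconcile Protocol 4.3.1, 4.3.2, 4.3.2.1 and 4.3.2.1.1 with SAP 4.3.2.2 on what is done and recorded at the ends of the strength range. No dose rule is proposed here.

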##### **4.3.2.3 Average Hb and Change from Baseline**

Average Hb values will also be summarized by Hb levels: < 10 g/dL, between 10 and 12 g/dL, and > 12 g/dL. The number and percentage of patients within each Hb level will be presented. The Hb level at evaluation period, at baseline and the change from baseline to evaluation period will be listed for all the patients.

##### **4.3.2.4 Patients with Dose adjustments**

Patients with dose adjustments during the core study period will be summarized descriptively, overall and by age-group.

### **4.3.3 Exploratory Efficacy Endpoints**

The patient if 4 years or older, the parent/guardian, and the nurse/site staff member who gives the injection will assess injection pain using a VAS scale 5 minutes following ESA administration, as appropriate. The assessments will take place during the screening period for all patients who received an ESA injection during either or both of the visits, and at Week 1 (Visit 3) and Week 9 (Visit 6). Injection pain data will be plotted by visit for each patient and separately for patient reported, nurse reported, and parent reported assessments. Descriptive summary statistics for the pain score assessed by nurse/ site staff, patient and parent respectively will be presented by visit. A plot of mean pain scores per assessor category per visit will be produced.

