The mechanism of anemia due to CKD in children is identical to that in adults. Treatment modalities are also identical (KDIGO 2012). Exogenous replacement of EPO by erythropoiesis-stimulating agents (ESAs) is an established method for anemia treatment in CKD in conjunction with iron supplementation (Locatelli et al. 2004). The currently available treatment options include short-acting human recombinant EPOs (epoetin alfa and epoetin beta), requiring several injections per week due to their short half-life, and longer-acting ESAs (hyperglycosylated [darbepoetin alfa] and pegylated [Mircera[®]]), which need less frequent dosing due to their prolonged half-life. Epoetin alfa/beta and darbepoetin alfa are approved treatments for anemia associated with CKD in pediatric patients. Several studies in pediatric patients with CKD have demonstrated that the safety profile of epoetin alfa/beta or darbepoetin alfa in pediatric patients is similar to that in adults (Gagnadoux et al. 1994; Van Damme-Lombaerts et al. 1994; Burke 1995; Sieniawska and Roszkowska 1997; Brandt et al. 1999; Greenbaum et al. 2000; Morgan et al. 2001; Seeherunvong et al. 2001; Geary et al. 2005; Warady et al. 2006; Warady 2015). The long-term safety and efficacy of darbepoetin alfa were assessed in a prospective registry study of 319 patients treated for up to 2 years (Schaefer et al. 2016). No new safety signals were found for darbepoetin alfa treatment, and anemia was effectively managed in these patients.

Similar to adults with CKD, many children with CKD undergoing hemodialysis (HD) or peritoneal dialysis (PD) require continuous long-term treatment with ESAs to maintain anemia correction. In addition, a significant number of children with reduced kidney function not yet on dialysis (CKD Stage \geq 3b) develop anemia and may need therapy with ESAs to raise hemoglobin (Hb) values (Koshy and Geary 2008).

Data on the epidemiology of CKD in children who are on dialysis are available from the North American Pediatric Renal Trials and Collaborative Studies (NAPRTCS 2014) and the United States Renal Data System (USRDS 2016). Information regarding pediatric patients who receive maintenance HD or PD has been captured since 1992. Children

with CKD represent a very small percentage of the total CKD population (NAPRTCS 2014 and USRDS 2016).

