Appendix 1 Schedule of Activities Core Period (Week –3 to Week 21) (cont.)

- ^h *Systolic* and diastolic blood pressure and pulse rate will be recorded while the patient is if possible in a seated position, and they will be measured before blood sampling. The blood pressure should be measured at least twice and the average of these measurements should be recorded. An appropriate-sized cuff should be used. Blood pressure should be determined before and after the dialysis session for patients with HD. Body weight will also be recorded (*after dialysis for patients on HD*).
- ⁱ Includes Hb, RBC, and absolute reticulocyte count. Samples should always be obtained on the same day of the week, *if possible*, prior to injection of Mircera and, for patients on HD, before dialysis.
- ^j Serum creatinine should be measured only for patients not on dialysis. eGFR will be calculated using the Bedside Schwartz formula (see [Appendix 3](#)).
- ^k Includes serum ferritin, serum iron and TSAT. TSAT will be calculated as described in [Appendix 3](#) with either serum transferrin or total iron-binding capacity. The percentage of hypochromic red blood cells may be determined instead of TSAT.
- ^l Includes leukocytes plus differential, AST, ALT, serum albumin, ALP, C-reactive protein, potassium, phosphorus, calcium, and platelets.
- ^m Anti-EPO and anti-Mircera antibody samples should be collected prior to study drug administration.
- ⁿ Injection pain will be assessed by the patient, parent/guardian, and nurse/site staff member as appropriate. Children under the age of 4 will not be asked to rate their own pain. As much as possible, the same nurse/site staff member should rate pain at every visit. The assessments will take place approximately 5 minutes after study drug injection. Assessment of ESA injection pain during the screening period will be assessed in all patients who receive an ESA injection during either or both of the screening visits.
- ^o Parentheses indicate that the assessment is optional. The assessment at the screening visit is only necessary if ESA drug has been injected on that day. Therefore, not all patients will assess injection pain.
- ^p All concomitant therapy administered within 3 months before screening or during the screening or treatment periods should be reported.
- ^q Prior to initiation of study drug, report only serious adverse events caused by a protocol-mandated intervention.

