### **2.2.3 Exploratory Endpoints**

Assessment of injection pain using a VAS scale 5 minutes following ESA administration will be done by the patient if 4 years or older, the parent/guardian and the nurse/site staff. The assessments will take place during the screening period for all patients who received an ESA injection during either or both of the visits, and at Week 1 (Visit 3) and Week 9 (Visit 6). Injection pain data will be plotted by visit for each patient and analyzed in an exploratory manner. Mean injection pain scores will be plotted for all patients per assessor category and per visit.

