  - m Anti-EPO and anti-Mircera antibody samples should be collected prior to study drug administration.
  - n Injection pain will be assessed by the patient, parent/guardian, and nurse/site staff member as appropriate. Children under the age of 4 will not be asked to rate their own pain. As much as possible, the same nurse/site staff member should rate pain at every visit. The assessments will take place approximately 5 minutes after study drug injection. Assessment of ESA injection pain during the screening period will be assessed in all patients who receive an ESA injection during either or both of the screening visits.
  - o Parentheses indicate that the assessment is optional. The assessment at the screening visit is only necessary if ESA drug has been injected on that day. Therefore, not all patients will assess injection pain.
  - p All concomitant therapy administered within 3 months before screening or during the screening or treatment periods should be reported.
  - q Prior to initiation of study drug, report only serious adverse events caused by a protocol-mandated intervention.
  - r *Treatment with ESAs should continue during the screening period at the previous dosing interval. Note that depending on the dosing interval, ESA treatment may or may not be administered the same day as the screening period visit.*
  - s At Visit 3 (Week 1), Visit 6 (Week 9), and Visit 8 (Week 17), samples should be drawn before the Mircera dose. At the patient's convenience, a sixth PK sample between 24 hours and 5 days after any one Mircera dose administration should also be collected. A minimum of one PK sample after treatment initiation is requested in patients younger than 2 years old; the sample on Week 1 can be omitted in these patients. The exact time of PK blood sampling must be recorded on the lab requisition form and the exact time of the preceding Mircera administration must be recorded on the appropriate page in the eCRF.

Study Period	Safety Extension Period 24 Weeks						
	10	11	12	13	14	15	16
Visit Number							
Name of the Visit Day (start of Week ...) a	Week 21 b	Week 25	Week 29	Week 33	Week 37	Week 41	Week 45 Final Safety Extension Visit c
Informed consent	x						
Physical examination d	x						x
Vital signs, weight e	x	x	x	x	x	x	x
Height	x						x
Hematology f	x	x	x	x	x	x	x
Serum creatinine g	x						x
Iron parameters h	x		x		x		x

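### The by-visit mean pain plot sets prior-ESA scores from a selected set of patients beside Mircera scores that carry no such selection, and no paired summary by previous ESA is planned

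*SAP*

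**What the plan says.** Injection pain is an exploratory endpoint, rated on a 10-cm VAS by the patient (from age 4), the parent or guardian, and the nurse or site staff member. Protocol 4.5.7 makes both the previous ESA injection and the Mircera injection targets of the rating.

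- **Who is rated at screening.** SAP 4.3.3: "The assessments will take place during the screening period for all patients who received an ESA injection during either or both of the visits". Protocol Appendix 1, footnote o: "The assessment at the screening visit is only necessary if ESA drug has been injected on that day". The same footnote in SAP Appendix 2 draws the consequence: "Therefore, not all patients will assess injection pain".
- **What decides it.** Footnote r of the schedule says that whether the ESA falls on a screening-visit day depends on its dosing interval. Protocol 1.1 describes the epoetins as "requiring several injections per week due to their short half-life" and contrasts them with longer-acting agents, including darbepoetin alfa, that are given less often.
- **Who is rated on Mircera.** Ratings are made at Week 1 and Week 9. Both are scheduled dosing visits, and neither rating depends on having been rated at screening.
- **How it is summarised.** SAP 2.2.3: "Mean injection pain scores will be plotted for all patients per assessor category and per visit". SAP 4.3.3 adds descriptive statistics by visit and repeats the mean plot: "A plot of mean pain scores per assessor category per visit will be produced". It also plans individual displays: "Injection pain data will be plotted by visit for each patient and separately for patient reported, nurse reported, and parent reported assessments".
- **What is absent.** There is no within-patient ESA-to-Mircera difference and no restriction of the means to patients with both ratings. There is also no split of pain by previous ESA, because SAP 4.3.5 repeats only the primary endpoint and dose over time by subgroup.

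**The concern.** In a single-arm study the previous ESA is the only reference available for Mircera injection pain. The planned aggregate display puts screening visits and Mircera visits on one axis, but the patients behind the points are not the same. The screening points come from patients whose ESA schedule happened to meet a visit day. The Mircera points come from everyone still on treatment who can be rated.

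The selecting factor, dosing interval, is tied to the product. The product may itself be tied to pain: the title of a study in the protocol's reference list, cited in Protocol 4.5.7 for the VAS, reports more injection pain with darbepoetin than with epoetin beta in pediatric dialysis patients.

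A step between the screening and Mircera means could therefore reflect the drugs, the change in who was rated, or both. Protocol 5.3.5.13 keeps patient- and observer-reported scores out of the safety analyses, so for those scores the SAP 4.3.3 output is where readers will look. The primary endpoint, the starting-dose conclusion and the safety analyses are not affected.

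**Working it through.** The documents give no figure for injection pain, so there is none to reproduce. The check has three steps.

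**1. Patient sets by visit**

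| Visit | Injection rated | Condition for a score |
|---|---|---|
| Visits 1 and 2 (screening) | Previous ESA | ESA injected at that visit |
| Visit 3 (Week 1) | Mircera | None beyond the age limit for self-report |
| Visit 6 (Week 9) | Mircera | As Week 1, and still on treatment |

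The age limit applies at every visit, so it does not separate the sets. The condition on the ESA injection does.

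**2. What an unpaired comparison of means picks up (illustration)**

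Let *r* be the share of patients with a screening score. Let *d* be the difference in underlying pain score, rated minus unrated patients. Suppose there is no true drug difference, and let unrated patients have mean *a*.

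- Screening mean = *a* + *d*
- Week 1 mean = *r*(*a* + *d*) + (1 - *r*)*a* = *a* + *rd*
- Spurious gap, screening minus Week 1 = (1 - *r*)*d*

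Neither *r* nor *d* is given in the documents; the values below are assumptions.

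| *r* | *d* = -2 cm | *d* = -1 cm | *d* = 0 | *d* = +1 cm | *d* = +2 cm |
|---|---|---|---|---|---|
| 30% | -1.4 | -0.7 | 0 | +0.7 | +1.4 |
| 50% | -1.0 | -0.5 | 0 | +0.5 | +1.0 |
| 70% | -0.6 | -0.3 | 0 | +0.3 | +0.6 |

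The gap vanishes when *d* = 0 or *r* = 100%. A simulation with 40 patients and no true drug difference gave 0.70 cm at *r* = 30%, *d* = 1 cm, and 0.50 cm at *r* = 50%, *d* = 1 cm. The mean paired difference in the same simulated patients was zero to within 0.01 cm.

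**3. What pairing does and does not remove**

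Let *w* be the share of epoetin users among all patients and *w′* their share among paired patients. Let Δ_E and Δ_D be the mean within-patient differences (Mircera minus ESA) for former epoetin and darbepoetin users.

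- Overall paired mean = *w′*Δ_E + (1 - *w′*)Δ_D
- Same quantity at the enrolled mix = *w*Δ_E + (1 - *w*)Δ_D
- Difference between the two = (*w′* - *w*)(Δ_E - Δ_D)

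Pairing puts the same patients on both sides, which removes the gap in step 2. It does not change *w′*. If frequently dosed ESAs are over-represented among rated patients, the overall paired mean keeps that weighting. Reporting Δ_E and Δ_D separately deals with it.

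**The case against.** The strongest reply is that the plan makes no claim for this comparison to bias. Pain is not in the objectives and endpoints table, the analysis is descriptive, and no ESA-versus-Mircera difference, test or conclusion is specified. The individual plots let a reader follow each patient from ESA to Mircera, and with about 40 patients that is real mitigation. The footnotes say openly that some patients will not be rated. All of this stands, and it keeps the point small. It does not remove it: individual plots give no summary, and the only aggregate display is the one that mixes the sets.

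A reader might go further and try to quantify the bias from dosing frequency. If visit days were unrelated to ESA days, three injections a week against one would give rating chances of 3/7 and 1/7. With equal numbers on each product, epoetin users would then make up (3/7)/(3/7 + 1/7) = 75% of the screening ratings. The documents do not support that step. Footnote a of the schedule says the ESA interval is to be taken into account when Visits 1, 2 and 3 are planned, and that it sets the gap between Visits 2 and 3. That could bring an infrequent ESA dose onto a visit day more often than chance would. The equal split is not in the documents either.

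The link from product to pain is also thin. It rests on one reference title, which names epoetin beta only and gives no effect size. Previous treatment may also be epoetin alfa or, in the SAP, a biosimilar.

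Finally, a reader might take the paired difference as free of confounding. It is not: ratings are open-label and the ESA always comes first.

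**Conclusion.** The point holds as a minor weakness in an exploratory summary. The by-visit means rest on different patient sets at screening and on Mircera, the difference depends on ESA dosing interval and hence product, and the SAP has no paired summary or split by previous ESA to separate this from a drug difference.

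Its size and direction cannot be derived from the documents. The -1.4 to +1.4 cm range rests on the assumed values of *r* and *d*, and zero is possible. A statement that the plan performs a confounded ESA-versus-Mircera comparison would go too far; the plot only invites that reading.

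**What to change.** In SAP 4.3.3, and in matching words in SAP 2.2.3:

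- For each assessor, summarise the within-patient difference in patients with both ratings: the Mircera score at Week 1 minus that patient's mean screening ESA score, and likewise for Week 9. State the number paired.
- Present it by previous ESA (epoetin versus darbepoetin, using the SAP 4.3.5 grouping) as well as overall.
- Limit any plot that shows ESA and Mircera means together to the paired patients. Keep all-patient means for the Mircera visits only. Show n at each visit.
- Describe the result as exploratory, open-label and fixed-order.

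The cost is SAP wording and one table or plot, from data already collected. The comparison will use fewer patients: at the assumed 30% to 70% rated, 12 to 28 of 40 before any missing Mircera scores. The split by previous ESA will be smaller still.
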